6.1 Analysis Populations

6.1.1 Intent to Treat (ITT)

Intent-to-Treat (ITT) population: includes all subjects who were randomized and have at least one post-treatment assessment. Analysis of the ITT population will be used for primary efficacy analyses and will be performed for all efficacy endpoints, analyzing subjects under the treatment to which they were randomized.

6.1.2 Per Protocol (PP)

Per Protocol (PP) population: includes all of the subjects in the ITT population that remained in the study through Visit 5 (Postoperative Day 14) and who did not deviate from the protocol in any way likely to seriously affect the primary outcome of the study. Analyses using the PP population will be used to supplement the ITT analysis, analyzing subjects according to the treatment received.

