3.2.3 Rescue Therapy

Subjects will be assessed at Visits 3 through 6 (Postoperative Days 1, 7, 14, and 28) for rescue. A study eye with greater than anticipated inflammation at Visit 3 or, at the following visits, a worsening or no change of the grade of inflammation compared to the previous visit may be eligible for rescue therapy. In some cases a persistent or worsening inflammation may be due to a lack of compliance. This should be explored and rectified. If the Investigator deems rescue necessary, the choice of rescue therapy and dosing shall be determined by the Investigator. Subjects requiring rescue therapy for inflammation will stop treatment with study medication. The subject should be exited from the study and the reason selected for exit should be “rescue therapy” in the eCRF. This should not be reported as an AE unless determined to be an SAE.

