5.2.2 Secondary Efficacy Endpoints

Secondary efficacy endpoints include the following:

- Mean grade of ACI at Visits 4 and 6 (Postoperative Days 7 and 28)
- Proportion of subjects with Grade 0, Grade 1, Grade 2, Grade 3, and Grade 4 converted ACI at each visit (Postoperative Days 7, 14, and 28)
- Presence/absence and total area, if present, of synechiae at each visit (Postoperative Days 7, 14, and 28)
- Presence/absence and total number, if present, of precipitates on the implant and cornea at each visit (Postoperative Days 7, 14, and 28)

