9.2.2 Treatment Compliance

Study drug compliance will be calculated for each subject by taking into account whether a subject takes all doses of study drug as instructed. Compliance will be based solely on the subject diaries. The study drug compliance rate will be presented overall, at Visit 4, Visit 5 and Visit 6. The study drug compliance rate for Visit 5 will be calculated by dividing the total number of dosing recorded in the diary for the subject for that period by the total number of days times 4 and then multiplying by 100. The first day of dosing will be ignored entirely, since subjects may be compliant with any number of doses.

The overall study drug compliance rate will be calculated by dividing the total number of dosing recorded in the diary for a subject across the entire treatment period by the total number of days times 4 for days \leq 14, times 2 for days between days 15 and 21 and times 1 for days between 22 and 28 and then multiplying by 100. The first day of dosing will be ignored entirely, since subjects may be compliant with any number of doses. The number and percentage of subjects in each of the following compliance rate categories will also be reported: (\leq 50%, 51-60%, 61-70%, 71-80%, 81-120%, and $>$ 120%). Percentages will be calculated out of the number of subjects who returned diaries from that dosing period. The number and percentage of subjects in each compliance rate category will be presented overall, at Visit 4, Visit 5 and Visit 6.

10 Statistical Analyses

All efficacy analyses will use a 2-sided alpha = 0.05 test unless otherwise stated. No adjustments will be made for multiplicity testing.

Analyses will be performed on the ITT and PP analysis set for both the primary efficacy endpoint and secondary efficacy endpoints. The safety analyses will be performed on the SAF.

All continuous efficacy endpoints will be summarized graphically by treatment group displaying the mean and corresponding standard errors at each time point for the primary efficacy endpoint or line graphs of the continuous secondary efficacy endpoints over scheduled time.

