10.2 Secondary Efficacy Analysis

All secondary analyses will be based on the ITT and PP.

As a secondary analysis, the analysis of the observed mean grade of ACI will be repeated as above for Visits 4 and 6 (Postoperative Days 7 and 28, respectively).

Additional secondary analyses include:

- The proportion of subjects with ACI of Grade 0, Grade 1, Grade 2, Grade 3, and Grade 4 for each visit (Postoperative Days 7, 14, and 28)
- The proportion of subjects with presence/absence and total area, if present, of synechiae in the study eye for each visit (Postoperative Days 7, 14, and 28)
- The proportion of subjects with presence/absence and total number, if present, of precipitates on the implant and cornea in the study eye at each visit (Postoperative Days 7, 14, and 28)

For each of the above endpoints, treatment groups will be compared using the Pearson Chi-squared test or Fisher's exact test as appropriate. Differences between the

proportions of treatment groups and 95% confidence interval about the differences will be presented.

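### The single per-protocol set requires staying to Visit 5 but is also used for Day 7 endpoints, so the Day 7 per-protocol comparison leaves out children rescued at Visit 4 and selects on a consequence of its own outcome

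*SAP*

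**What the plan says.** **The set.** SAP 6.1.2 gives one PP definition. It "includes all of the subjects in the ITT population that remained in the study through Visit 5 (Postoperative Day 14") and whose deviations, if any, were not likely to seriously affect the primary outcome. Protocol 7.5 says the same. Neither document has a version for another visit.

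**Where it is used.** SAP 10 states: "Analyses will be performed on the ITT and PP analysis set for both the primary efficacy endpoint and secondary efficacy endpoints". SAP 10.2 repeats it: "All secondary analyses will be based on the ITT and PP". The secondary endpoints in SAP 5.2.2 include "Mean grade of ACI at Visits 4 and 6 (Postoperative Days 7 and 28"), and also the Day 7 grade proportions, synechiae and precipitates. ACI is anterior chamber inflammation. For the mean grade, SAP 10.2 says that "the analysis of the observed mean grade of ACI will be repeated as above for Visits 4 and 6".

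**Rescue.** Protocol 3.2.3: "Subjects will be assessed at Visits 3 through 6 (Postoperative Days 1, 7, 14, and 28) for rescue". After Visit 3, an eye with "a worsening or no change of the grade of inflammation compared to the previous visit may be eligible for rescue therapy", and the Investigator decides. For a rescued child study drug stops, and "The subject should be exited from the study and the reason selected for exit should be" rescue therapy. Protocol 3.2.4 and SAP 5.7 both list the need for rescue among the reasons for mandatory discontinuation.

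**The concern.** A per-protocol set for a given visit should depend on what happened up to that visit. Here, membership in the Day 7 comparison depends on still being in the study a week later. One route out in that week is rescue at Visit 4, and eligibility for that rescue rests on how the Day 7 grade compares with the previous visit. The Day 7 grade can therefore lead to the child's removal from the Day 7 analysis.

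The protocol's Summary of Changes suggests how this arose. Amendment 6 moved the primary endpoint from Day 7 to Day 14 and moved the PP retention point with it. Day 7 became a secondary visit that falls before the retention point.

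What is at stake is the value of the Day 7 PP result as a supplement to the intent-to-treat (ITT) result. If early treatment failures differ between arms, a PP set that drops them is a biased supplement.

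**Working it through.** **1. The plan's own figure.** The only stated power is for the Day 14 primary endpoint (SAP 5.4: 60 per group, SD 0.47, margin 0.35, true difference 0, two-sided alpha 0.05, 98% power).
- Standard error = 0.47 × √(2/60) = 0.0858.
- 0.35 / 0.0858 − 1.96 = 2.12, which gives power of 98.3%. The noncentral t with 118 df gives 98.1%.

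The 98% is reproduced. The documents give no figure for the Day 7 PP analysis.

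**2. The textual check.** Take a child rescued at Visit 4.
- The Day 7 grade is observed at that visit, on assigned drug.
- Rescue forces exit, so the child is not in the study through Visit 5 and is not in the PP set.
- The same PP set is used at Day 7, so the observed Day 7 data are left out.
- The PP no-imputation rule (SAP 6.2) does not restore them. It concerns missing and post-rescue data, and this grade is neither.
- The ITT set (SAP 6.1.1) keeps the child, since it needs only randomization and one post-treatment assessment.

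The Day 14 PP analysis does not have this fault: a child who left at Visit 4 has no on-treatment Day 14 grade to lose.

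**3. Size of the shift.** Let r be the share of an arm rescued at Visit 4, m the Day 7 mean of the children not rescued, and g the grade gap between rescued and other children.
- Arm mean with the rescued children kept: m + r × g.
- Arm mean with them dropped: m.
- With a common g in both arms, dropping them takes (r_LE − r_PR) × g off the difference, LE (loteprednol) minus prednisolone.
- If m is also equal in both arms, the PP difference is 0.

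The documents give neither arm-level rescue rates nor Day 7 grades, so every input below is an assumption. Take mean grades of 2.5 (rescued) and 0.8 (others), so g = 1.7:
- 10% versus 4%: (0.10 × 2.5 + 0.90 × 0.8) − (0.04 × 2.5 + 0.96 × 0.8) = 0.970 − 0.868 = 0.102. Against the 0.35 margin, used only as a yardstick, that is 29%.
- 8% versus 4%: 0.04 × 1.7 = 0.068, or 19% of 0.35.

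| Rescue at Visit 4, LE vs prednisolone | Gap (grades) | Difference with rescued children kept | PP difference |
|---|---|---|---|
| 6% vs 6% | 1 to 2 | 0 | 0 |
| 8% vs 4% | 1.7 | 0.07 | 0 |
| 10% vs 4% | 1.7 | 0.10 | 0 |
| 4% vs 10% | 1.7 | −0.10 | 0 |
| 12% vs 6% | 1 to 2 | 0.06 to 0.12 | 0 |
| 18% vs 6% | 1 to 2 | 0.12 to 0.24 | 0 |
| 20% vs 4% | 1 to 2 | 0.16 to 0.32 | 0 |

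**4. Plausibility.** SAP 5.4 allows 12% for all dropout and rescue together: 0.12 × 140 = 16.8 children. With 1:1 allocation, 10% versus 4% averages 7% at this one visit, more than half of that allowance. Each of the last two rows averages 12% and would use all of it at Day 7, so those rows are extremes.

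**The case against.** The strongest reply is that little depends on this analysis. PP is declared a supplement to ITT, Day 7 is a secondary time point, and the only stated hypothesis (SAP 5.3) is at Day 14. The Day 7 ITT analysis uses observed grades and keeps these children. A single PP set tied to the primary outcome is also a coherent convention. All of this stands and limits the weight of the point. It does not remove the selection.

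A reader might infer more than the documents support:

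- **That the bias always favours non-inferiority.** It does so only if LE has more Visit 4 rescues. If prednisolone has more, the exclusion removes an LE advantage. With equal rates and gaps the difference is not shifted.
- **That the PP result would falsely confirm ITT.** In the illustration Day 7 ITT shows 0.10 and PP shows 0, so the loss is visible as a gap. SAP 10.1 asks for ITT/PP discrepancies to be explained. That sentence is written for the primary analysis, though SAP 10.2 repeats the method at Visit 4.
- **That children are excluded for a high grade as such.** The trigger is change from the previous visit plus Investigator judgement. A child at Grade 1 on both Day 1 and Day 7 may be eligible; one falling from 4 to 3 does not meet that criterion. Lower PP means are plausible but not established.
- **That every such child is free of deviations.** Protocol 3.2.3 notes that persistent inflammation may reflect poor compliance. Some of these children could fail the deviation criterion anyway, and would rightly stay out.

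**Conclusion.** The point holds on the text alone: the Day 7 PP comparison omits observed on-treatment data from children rescued at Visit 4, and so selects on a consequence of its own outcome. No other provision repairs this.

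Its numerical effect is conditional. It is about 0.07 to 0.10 grade under the two main illustrations, zero with equal rates and gaps, and of opposite sign if prednisolone has more rescues. These figures rest on assumed rescue rates, a common assumed grade gap, and equal means among children not rescued. They also ignore the site adjustment in the SAP 10.1 model.

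Neither the primary Day 14 ITT conclusion nor the Day 7 ITT analysis is affected. This is a cheap improvement to a supplementary analysis, not a threat to the trial's main result.

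**What to change.** In SAP 6.1.2 and 10.2, state that for Visit 4 endpoints the PP set is the ITT subjects in the study at Visit 4 with no major deviation up to Visit 4. Keep the Visit 5 definition for the primary endpoint. Settle this before the first tables by treatment; under SAP 11 the interim analysis already produces the full set.

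The change also restores children who leave between Visits 4 and 5 for other reasons, provided they have no major deviation up to Visit 4. It alters no rescue rule, visit, data collection or sample size.

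The cost is small but not nil: a second PP flag, a deviation review with a Visit 4 cutoff, and PP denominators that differ by visit. The disposition and demographic tables (SAP 7 and 8.1), which assume one PP set, need a note saying which set they describe.

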6.1.3 Safety (SAF)

Safety analysis population: includes all participants who received at least one dose of study drug.

All subjects in the Safety analysis population will be analyzed according to the treatment received. All safety and tolerability analyses will be based on the Safety analysis population.

6.2 Handling of Missing Data

For the primary efficacy endpoint analyzed using the ITT population, missing data and data from subjects placed on rescue medication prior to Day 14 will be analyzed using

the last observation carried forward (LOCF). For the PP analysis, missing data and data from subjects placed on rescue medication will not be imputed.

Data from unscheduled/repeated visits will be presented in listings and will be included in safety summaries for considering the worst-case scenario.

6.3 Changes in the Planned Analysis

Change from protocol: Investigation site is added as a covariate in the primary analysis model, and the model was changed from a one-way ANOVA to an ANCOVA model. Any deviations from this statistical analysis plan will be documented in the final clinical study report.

7 Subject Disposition

A disposition table of subjects will include the number and percentage of subjects in each of the following categories:

- Subjects randomized (ITT analysis population)
- Subjects treated (Safety analysis population)
- Subjects in the PP analysis population

Within each of the previous categories, the number and percentage of subjects who completed and discontinued from the study will be summarized.

The reasons for study discontinuation will also be summarized. The reason for discontinuation may include any of the following:

- Withdrew consent
- Lost to follow-up
- Administrative issue
- Adverse event
- Rescue Therapy
- Failure to follow required study procedures
- Investigator decision that it is not in the best medical interest of the subject
- Onset of menarche
- Other

Only 1 reason (primary) for study discontinuation will be recorded for each subject.

A listing will present data concerning subject disposition and other reasons for discontinuation

7.1 Protocol Deviations

The date of and reason for protocol deviations will be documented in all cases. Major protocol deviations will be finalized before the database lock. Major protocol deviations will be summarized. A listing of all protocol deviations will be presented.

8 Demographics and Baseline Characteristics

8.1 Demographics

Demographic characteristics including race, ethnicity, gender, iris color, and age will be summarized by treatment group for the ITT, PP and SAF. Age (\leq 3 years, $>$ 3 years), race, ethnicity, iris color, source of breast milk, and gender will be summarized as categorical variables, while age will also be summarized as a continuous variable. All percentages will be based on the number of randomized subjects. Comparability of baseline variables will be tested using two-sided t-test or Chi-square test, as appropriate.

8.2 Non-Ocular and Ocular Medical History

Non-ocular medical history will be listed by subject and summarized as categorical variables at the subject and event level by system organ class and preferred term for each treatment group. Ocular history will be listed and summarized similarly for study and fellow eyes separately.

8.4 Inclusion and Exclusion Criteria

A listing of inclusion and exclusion criteria along with date of informed consent will be listed by subject.

9 Treatments and Medications

9.1 Prior and Concomitant Medications

All medications will be coded using the World Health Organization (WHO) drug dictionary version 1Q2010. All non-study drugs (including prescribed and over the counter [OTC] medications) used within 30 days prior to study entry and all non-study drugs used during the course of the study will be collected on the eCRF.

Concomitant medication use will be summarized by the number and percentage of subjects taking each medication. Medications taken prior to study drug will be presented in a listing. Rescue medication will be listed and summarized, if appropriate.

9.2 Study Treatments

9.2.1 Extent of Exposure

Extent of exposure is defined as the total number of days from the first dose date to the last dose date, as recorded at the randomization study visit and the study exit eCRF page. Study drug exposure will be calculated based on subject diary data.

The extent of exposure and study drug exposure will be summarized in a table by summary statistics including the mean, standard deviation, median, minimum, and maximum exposure.

9.2.2 Treatment Compliance

Study drug compliance will be calculated for each subject by taking into account whether a subject takes all doses of study drug as instructed. Compliance will be based solely on the subject diaries. The study drug compliance rate will be presented overall, at Visit 4, Visit 5 and Visit 6. The study drug compliance rate for Visit 5 will be calculated by dividing the total number of dosing recorded in the diary for the subject for that period by the total number of days times 4 and then multiplying by 100. The first day of dosing will be ignored entirely, since subjects may be compliant with any number of doses.

The overall study drug compliance rate will be calculated by dividing the total number of dosing recorded in the diary for a subject across the entire treatment period by the total number of days times 4 for days \leq 14, times 2 for days between days 15 and 21 and times 1 for days between 22 and 28 and then multiplying by 100. The first day of dosing will be ignored entirely, since subjects may be compliant with any number of doses. The number and percentage of subjects in each of the following compliance rate categories will also be reported: (\leq 50%, 51-60%, 61-70%, 71-80%, 81-120%, and $>$ 120%). Percentages will be calculated out of the number of subjects who returned diaries from that dosing period. The number and percentage of subjects in each compliance rate category will be presented overall, at Visit 4, Visit 5 and Visit 6.

10 Statistical Analyses

All efficacy analyses will use a 2-sided alpha = 0.05 test unless otherwise stated. No adjustments will be made for multiplicity testing.

Analyses will be performed on the ITT and PP analysis set for both the primary efficacy endpoint and secondary efficacy endpoints. The safety analyses will be performed on the SAF.

All continuous efficacy endpoints will be summarized graphically by treatment group displaying the mean and corresponding standard errors at each time point for the primary efficacy endpoint or line graphs of the continuous secondary efficacy endpoints over scheduled time.

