The subject will receive the first dose of study drug by the unmasked designee at the end of the surgery. Either the unmasked designee or the subject's parent/legal guardian will then administer 1 to 2 drops of study drug to the lower cul-de-sac of the study eye once in the evening on the day of surgery and then four times a day (QID), at approximately four hour intervals, beginning on the morning after surgery. QID dosing will continue until postoperative day 14, including dosing at appropriate time intervals on the day of a visit. Treatment will be tapered from QID to twice a day (BID) during the interval between postoperative days 15 and 21. Treatment will be further tapered from postoperative day 22 until day 28 to once a day (QD) with the last dose being administered on the day prior to Visit 6 (Postoperative Day 28).

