4.10 Selection of Dose

The dose regimen in this study is the same regimen across both treatment groups (ie, 1 to 2 drops of study drug instilled in the study eye, QID, at approximately 4 hour intervals). This regimen was selected for the study based on the dose regimen of the currently marketed *Lotemax* (LE Ophthalmic Gel, 0.5%) and is also the treatment recommended in the Package Insert (PI) and Summary of Product Characteristics (SmPC) of the comparator drug.

Based on the standard of care for the treatment of postoperative inflammation in the US, both treatment groups will be dosed QID for the first 14 days and then tapered to BID from postoperative days 15 through 21 and the further tapered to QD from postoperative day 22 until the day prior to Visit 6 (Postoperative Day 28).

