7.6.5 Treatment Compliance

Treatment compliance will be assessed as the percentage of prescribed instillations received and will be presented using discrete summary statistics in the following categories: ($\leq 50\%$, $51\text{-}60\%$, $61\text{-}70\%$, $71\text{-}80\%$, $81\text{-}120\%$, and $> 120\%$). Percentages will be calculated out of the number of subjects who returned diaries from that dosing period. The number and percentage of subjects in each compliance rate category will be presented.

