5.9 Dose Adjustment/Modifications

Treatment will be tapered from QID to BID during the interval between postoperative days 15 and 21. Treatment will be further tapered to QD from postoperative day 22 until day 28, with the last dose being administered on the day prior to Visit 6 (Postoperative Day 28).

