5.10 Treatment Compliance Follow-up

In order to assess compliance of treatment administration, subject/subject's parent/legal guardian will be instructed to record the date and time of each study drug administration on a diary provided by the Sponsor.

6 General Statistical Considerations

All statistical analyses will be conducted using SAS Version 9.4 or higher.

Continuous data will be summarized using descriptive statistics: n, mean, standard deviation, median, minimum, and maximum. Means and medians will be presented to 1 more decimal place than the recorded data. Standard deviations will be presented to 2 more decimal places than the recorded data. Minimum and maximum values will be presented using the same number of decimal places as the recorded data. Categorical data will be summarized using counts for each category and corresponding percentages. Percentages will be presented to 1 decimal place. Confidence intervals will be presented using the same number of decimal places as the parameter (i.e. mean).

All statistical analyses will generally include summaries by treatment group or by treatment group and scheduled time point, as appropriate.

In general, the baseline value for a variable is defined as the last observation prior to the first dose of double masked study medication (Day 0), including the screening value, if necessary.

Study Day 0 is defined as the date on which a subject was randomized and took the first dose of double masked study medication. Other study days are defined relative to the Study Day 0 as Dose Date – Day 0 date + 1. The visit window for Day 7 is ± 2 , for Day 14 is ± 3 , for Day 28, 42, is ± 7 , and for Day 90 is ± 14 .

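### SAP 9.2.2 divides Visit 5 doses by four a day, although Visit 5 may fall on twice-daily Days 15-17 (minor; descriptive compliance table only)

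*SAP*

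**What the plan says.** - **Visit 5 rate.** SAP 9.2.2 divides the doses recorded "for the subject for that period by the total number of days times 4 and then multiplying by 100". The start and end of the period are not given. The next sentence adds "The first day of dosing will be ignored entirely", which would also fit a period starting on Day 1.
- **Overall rate.** The same section uses 4 doses a day up to day 14, then "times 2 for days between days 15 and 21 and times 1 for days between 22 and 28". Rates are reported overall and at Visits 4, 5 and 6. No denominator is given for Visits 4 and 6.
- **Protocol definition.** Protocol 7.6.5 states: "Treatment compliance will be assessed as the percentage of prescribed instillations received".
- **Schedule.** Protocol 3.1: "QID dosing will continue until postoperative day 14, including dosing at appropriate time intervals on the day of a visit". SAP 5.9: "Treatment will be tapered from QID to BID during the interval between postoperative days 15 and 21".
- **Windows.** Visit 4 is Day 7 ±2 (Days 5-9) and Visit 5 is Day 14 ±3 (Days 11-17), per Protocol 5.1.4 and 5.1.5 and SAP section 6.
- **Diaries.** A new diary is handed out at Visits 3, 4 and 5 (Protocol 5.1.3 to 5.1.5).
- **Precedence.** SAP section 3 says that the SAP overrides the protocol's statistical methods. SAP 6.3 lists no change to compliance.

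**The concern.** A rate reported visit by visit, from diaries renewed at each visit, is naturally read as covering the days up to that visit. On that reading, a late Visit 5 brings in days on which two doses were prescribed but four are expected. A child who did everything asked then looks partly non-adherent. The result disagrees with the protocol's definition and with the overall rate in the same SAP section. Because the SAP takes precedence and records no intended change, the four-a-day formula would be the one programmed.

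The Visit 5 rate describes adherence in the run-up to the primary Day 14 grade. Readers of a non-inferiority trial look at that figure when they ask whether similar results could reflect under-dosing.

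**Working it through.** The documents state no compliance figure, so there is none to reproduce.

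**Inputs.** Prescribed doses per postoperative day are 4 on Days 1-14 and 2 on Days 15-21 (Protocol 3.1 and 4.10; SAP 5.9). Visit 4 falls on Days 5-9 and Visit 5 on Days 11-17. The categories are those of SAP 9.2.2. The period is undefined, so each plausible reading is an assumption and is shown separately.

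**Formulas.** SAP score = doses recorded / (4 × days). Protocol rate = doses recorded / doses prescribed.

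**Full adherence.** Take Visit 4 on Day 7, Visit 5 on Day 17, and count Days 8-17. Prescribed doses are 7 × 4 + 3 × 2 = 34. The SAP denominator is 10 × 4 = 40. The SAP score is 34/40 = 85.0%; the protocol rate is 34/34 = 100%.

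The same calculation over the windows (ranges cover Visit 4 on Days 5 to 9) gives these SAP scores for a child who takes every dose:

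| Period counted | Visit 5 on Day 15 | Day 16 | Day 17 |
|---|---|---|---|
| Day after Visit 4 to Visit 5 | 91.7-95.0% | 85.7-90.9% | 81.25-87.5% |
| Visit 4 to day before Visit 5 | 100% | 92.9-95.5% | 87.5-91.7% |
| Day 1 to Visit 5 | 58/60 = 96.7% | 60/64 = 93.8% | 62/68 = 91.2% |
| Day 1 to day before Visit 5 | 56/56 = 100% | 58/60 = 96.7% | 60/64 = 93.8% |
| Either start, stopping at Day 14 | 100% | 100% | 100% |

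The lowest value is Visit 4 on Day 9 with Visit 5 on Day 17: (5 × 4 + 3 × 2)/(8 × 4) = 26/32 = 81.25%. For Visit 5 on Days 11-14, every reading gives 100%. So full adherence scores below 100% on 3, 2 or 0 of the 7 allowed days, according to the reading. It always stays in the 81-120% category.

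**Missed doses.** The table below gives the fewest missed doses that bring the SAP score to 80.0% or less while the protocol rate is at least 81%, with Visit 5 on Day 17.

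| Period counted | Missed doses | Example |
|---|---|---|
| Day after Visit 4 to Visit 5 | 1-4 | Visit 4 on Day 9: 25/32 = 78.1% against 25/26 = 96.2%. Visit 4 on Day 7: 32/40 = 80.0% against 32/34 = 94.1% |
| Visit 4 to day before Visit 5 | 3-6 | Visit 4 on Day 7, four missed: 32/40 = 80.0% against 32/36 = 88.9% |
| Day 1 to Visit 5 | 8 | 54/68 = 79.4% against 54/62 = 87.1% |
| Day 1 to day before Visit 5 | 9 | 51/64 = 79.7% against 51/60 = 85.0% |

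**Over-dosing.** The error also runs the other way. A child wrongly kept on four doses a day over Days 10-17 scores 32/32 = 100%, but received 32/26 = 123.1% of the prescribed doses, which belongs in the over-120% category.

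**The case against.** The strongest reply is that the period may be meant to stop at Day 14. The overall rate in the same section cuts there, and the SAP revision history pairs Visit 5 with Day 14 in its entry for 9.2.2. On that reading four a day is exactly right. This stands as a possible reading, but the text of 9.2.2 does not state it, and reporting by visit from diaries renewed at each visit points the other way. Two programmers could follow the section and produce different tables.

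It is also fair that the largest shifts need visits at the edges of their windows, and that 3 of 7 counts allowed days and not children. The documents do not say how many children will be seen on Days 15-17.

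Three stronger conclusions might be inferred, and the documents do not support them:

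- **The trial result is affected.** Neither per-protocol definition (Protocol 7.5, SAP 6.1.2) states a compliance threshold, no efficacy model uses compliance, and both arms share the formula and the windows.
- **The day cuts are off by one.** SAP section 6 says "Other study days are defined relative to the Study Day 0 as Dose Date" minus the Day 0 date plus 1, which would make postoperative Day 14 study day 15. But 9.2.2 does not invoke that rule, and its cuts match the postoperative days of SAP 5.8.1 and 5.9.
- **Children will switch to twice daily on the wrong day.** The Visit 4 reminder in Protocol 5.1.4 speaks of a further week without a calendar day. It only repeats a schedule fixed elsewhere: Protocol 4.10 has both arms "dosed QID for the first 14 days and then tapered to BID from postoperative days 15 through 21", Protocol 4.3 agrees, the Visit 3 instruction covers two weeks, and sites enter the dosing dates in the diary beforehand (Protocol 8.2).

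**Conclusion.** The point holds as a minor one. Taken as a rule for the days up to Visit 5, the SAP formula gives a wrong figure for children seen after Day 14. Full adherence scores about 81% to 97% whenever a twice-daily day is counted, and between 1 and 9 missed doses, depending on the reading, can put a child seen on Day 17 one category too low. This rests on the assumption that the period extends past Day 14; if it does not, the only fault is that the period is undefined. The number of children affected cannot be worked out from the documents. The consequence is confined to a descriptive compliance table.

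**What to change.** In SAP 9.2.2, define the Visit 5 rate, and likewise those for Visits 4 and 6, as follows:

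> Diary doses divided by the doses prescribed on the days of that diary period, times 100. Prescribed doses are 4 per day through postoperative Day 14, 2 per day on Days 15-21, and 1 per day on Days 22-28 up to the day before Visit 6.

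These are the same postoperative-day cuts as in the overall rate. The Day 28 limit matters because Visit 6 may fall as late as Day 35, while Protocol 4.3 and SAP 5.9 end once-daily dosing by Day 28.

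State the first and last day of each visit period, including which period the visit day belongs to. Dosing continues on visit days and a new diary is issued at the visit, so that day's recorded and prescribed doses should go to the same period.

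With this rule the worked example becomes 34/34 = 100%, and full adherence scores 100% for Visit 5 on any of Days 11-17. The cost is one SAP formula and one line defining the periods. Diary and visit dates are already collected, and no protocol change is needed.
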